#### 9.4 Record keeping and access to source data

The Investigator/Institution should permit study-related monitoring, audits, IRB review, and RA inspections and should provide direct access to the source data/medical record including the identity of all participating subjects (sufficient information to link records, i.e. eCRF, medical records, original signed informed consent forms and detailed records of study product accountability). The records should be retained by the Investigator as required by local legislation and international guidelines. Any transfer of responsibility for storage of the records should be documented and the Sponsor should be informed in writing.

The Sponsor should verify that each subject has consented in writing to direct access to the original medical record/source data (by the use of written subject information and signed informed consent). The data recorded in the eCRFs will be checked for consistency with the source documents/medical record by the monitor during monitoring (source data verification; SDV). In order to be able to perform SDV, information about each subject's participation in the study has to be detailed in the medical record.

#### 9.5 Document and data retention

All records pertaining to the conduct of the study, including signed eCRFs, informed consent forms, study product accountability records, source documents, and other study documentation must be retained for as long as is specified in the CTA. Measures should be taken to prevent accidental or premature destruction of these documents (e.g. protection against damage and unauthorized access, preferably by storage in a fire-proof cabinet).

It is the Investigator's responsibility to inform the Sponsor in writing if the Investigator file is moved or if the responsibility for the documents is transferred to someone else.

Doc id 43USCH1702 Protocol 👶 GALDERMA

Print date:

2021-02-09 21:57

# 10. Statistical Methods

## 10.1 General

Version: 5.0

Title
43USCH1702 Protocol

Doc id

Print date:

2021-02-09 21:57

2021-02-09 21:57

#### 10.5 Safety analysis

Number and percentage of subjects reporting each pre-defined, expected, post-treatment symptoms, as collected in the 28-day diary,

All AEs will be coded according to MedDRA and summarized by system organ class (SOC), preferred term (PT) and treatment.

A summary of all AEs will be provided, which will include:

- number of subjects with at least one AE and number of events (in total as well as serious AEs)
- number of subjects with at least one related TEAE and number of events (in total as well as serious AEs)
- number of subjects with at least one un-related TEAE and number of events (in total as well as serious AEs)
- number of subjects who did not have an AE

The number of subjects with AEs related to study product or injection procedure as well as the number of events will be summarized by SOC, PT, and severity. In addition, for related AEs the number of days to onset and the duration of event will be summarized by SOC and PT using mean, SD, min, max and median. Action taken for related AEs will also be summarized. Serious AEs will be listed.

Non-related AEs will be summarized by SOC, PT, and intensity.

To evaluate consistency of AEs across different subgroups, AEs will also be summarized by subgroups defined as described in Section 3.1.4.

Palpation, movement, function and sensation assessments will be presented in frequency tables by visit.

GALDERMA
Title
43USCH1702 Protocol

#### 10.8 Withdrawals and deviations

All withdrawn subjects will be listed individually, including at least subject number, date and reason for withdrawal, and last visit performed.

# 11. Protection of personal data

All processing of personal data must be carried out in accordance with national legislation concerning the protection of personal data. The Institution and the Investigator are responsible for complying with all requirements pursuant to national legislation in which the Institution and the Investigator are located. The Sponsor will ensure that all requirements for data processing are fulfilled.

The Investigator understands that clinical studies conducted under an IDE are exempt from the study subject identifier confidentiality provisions of the Health Insurance Portability and Accountability Act of 1996 (HIPAA), and the study subject should be made aware of this exception in the informed consent. The Institution and Investigator are jointly responsible for providing sufficient information to all subjects to enable them to give their informed consent not only to the participation in the investigation, but also to the processing of Personal Data. Such information includes information regarding the purposes of the processing, the length of time during which Personal Data will be stored, the right of access to stored Personal Data and the right to correction or purging of incorrect or obsolete Personal Data. A subject may also withdraw his or her consent at any time.

A subject who withdraws his or her consent to the processing of Personal Data must be considered to have withdrawn from the investigation but the data collected until the consent was withdrawn may be used in the statistical analyses.

Authorized representatives from the Sponsor or a RA may visit the investigational site to perform audits/inspections, including source data verification, i.e., comparing data in the subjects' medical records and the eCRF. Data and information will be handled with strict confidentiality.

# 12. Quality Control and Quality Assurance

#### 12.1 Quality control

On-site monitoring of the study will be arranged by the Sponsor according to GCP guidelines to verify that the rights and well-being of the subjects are protected, the reported data are accurate, complete, verifiable from source documents, and that the conduct of the study complies with the approved CIP, subsequent amendment(s), GCP and the applicable regulatory requirements.

Any CIP deviation should be reported in the eCRF, which will be verified, discussed, and collected, by the monitor and appropriate actions will be taken. The Investigator is responsible for promptly reporting any deviations from the CIP that affects the rights, safety or well-being of the subject or the scientific integrity of the study, including those, which occur under emergency circumstances, to the Sponsor as well as the IRB if required by national regulations. Deviations will be reviewed to determine the need to amend the CIP or to terminate the study. Handling of CIP deviations will be performed as described in the monitoring manual.

#### 12.2 Quality assurance

The study site may be subject to quality assurance audit by the Sponsor as well as inspection by appropriate RA. It is important that the Investigator and other relevant study site personnel are available during the monitoring visits, possible audits, and inspections, and that sufficient time is devoted to the monitoring process.

Each participating member of the study site team should provide a curriculum vitae (CV) or equivalent that demonstrates their qualifications to conduct the study.

It is the responsibility of the Investigator to ensure that all personnel involved in the study are fully informed of all relevant aspects of the study, including detailed knowledge of and training in all procedures to be followed. All Investigators and other responsible persons should be listed together with their function in the study on a signature and delegation log.

Effective

Version: 5.0

Title
43USCH1702 Protocol

Doc id

2021-02-09 21:57

Print date:

2021-02-09 21:57

# 15. Suspension or Premature Termination

The Sponsor will suspend or terminate the study when so instructed by the IRB or FDA, or if it is judged that the subjects are subjected to unreasonable risks, or for valid scientific or administrative reasons.

The Sponsor may also decide to close a single study site due to unsatisfactory subject enrollment or non-compliance with the CIP, GCP, or applicable regulatory requirements.

In the event of premature termination, the Sponsor will provide information on the handling of currently enrolled subjects who have not completed the study.

Title
43USCH1702 Protocol

Doc id

2021-02-09 21:57

Print date:

Page 69 of 72

Title
43USCH1702 Protocol Doc id 🚣 GALDERMA

[figure not shown]
Print date:

2021-02-09 21:57

# 17. Appendices

• GALDERMA	Title 43USCH1702 Protocol	Doe id
------------	---------------------------	--------

		Print date:	2021-02-09 21:57
♣ GALDERMA	43USCH1702 Protocol	Doc id	
 			

1.0 PURPOSE

This SAP describes the methods to be used in the analysis of study data from clinical protocol 43USCH1702 titled "A randomized, no-treatment-controlled, evaluator-blinded, multicenter study to evaluate the effectiveness and safety of Restylane® Defyne in the chin for augmentation and correction of Chin Retrusion" in order to answer the study objective(s), and is based on version 3.0 of the study protocol, dated 05JUL2018.

Populations for analysis, data handling rules, statistical methods, and formats for data presentation are described within this document. The statistical analyses and summary tabulations described in this SAP will provide the basis for the results sections of the CSR for this study. The SAP outlines any differences in data analysis methods relative to those planned in the study protocol. Any changes to the data analysis methods after the SAP is finalized will be described in the CSR.

2.0 ACRONYMS

Below is the list of acronyms that will be used throughout this document.

Abbreviation	Description
AE	Adverse Event
ATC-4	Anatomical Therapeutic Chemical 4th level
BMI	Body Mass Index
BOCF	Baseline Observation Carried Forward
CDISC	Clinical Data Interchange Standards Consortium
CSR	Clinical Study Report
G	Gram
eCRF	Electronic Case Report Form
ET	Early termination
eCTD	Electronic Common Technical Document
FST	Fitzpatrick Skin Type
GAIS	Global aesthetic improvement scale
GCRS	Galderma Chin Retrusion Scale
ICH	International Conference on Harmonisation
ICF	Informed Consent Form
IP	Investigational Product
IPR	Independent Photographic Reviewer
IRE	Injection Related Events
ISO	International Organization for Standardization
ITT	Intention-to-treat
MedDRA	Medical Dictionary for Regulatory Activities
PP	Per Protocol
PT	Preferred Term
SAE	Serious Adverse Event
SAP	Statistical Analysis Plan
SD	Standard Deviation
SOC	System Organ Class

	THE
🖧 GALDERMA	43USCH1702 Statistical Analysis Plan

Abbreviation	Description
SOP	Standard Operating Procedure
ТС	Telephone Call
TW	Thin Wall
WHO	World Health Organization
Тх	Treatment

3.0 OVERALL STUDY DESIGN AND OBJECTIVE

3.1 Study Objectives

3.1.1 Primary Effectiveness Objective

The primary objective of the study is to evaluate the effectiveness of *Restylane® Defyne* versus a no-treatment control in the correction of chin retrusion by comparing response rates, defined by at least 1 point improvement from baseline using

, as assessed by the Blinded Evaluator, at 12 weeks after last injection for the treatment group or after baseline if randomized to no treatment.

3.1.2 Secondary Effectiveness Objectives

The secondary objectives of this study are:

Title 43USCH1702 Statis	tical Analysis Plan	Doc id

3.1.3 Safety Objectives

- The safety objectives of this study are:
- i) To evaluate all adverse events (AEs) and pre-defined, injection related events (IREs) reported

3.2 Study Design and Study Procedures

This is a randomized, evaluator-blinded, parallel group, no-treatment control, multi-center study to evaluate the effectiveness and safety of Restylane® Defyne for chin augmentation and correction of Chin Retrusion.

3.3 Treatments and Assignment to Treatments

		-								
Approximately 14	40	subjects,				will	be	enrolle	ed	and
randomized		0	Df	treatment	to	Restylane	۶D	efyne	or	no-
treatment-control										

4.0 GENERAL ANALYSIS CONVENTION

Data collected in this study will be documented using summary tables and subject data listings. Continuous endpoints will be summarized using descriptive statistics, e.g. number of subjects, mean, median, standard deviation, minimum and maximum values. Categorical endpoints will be presented in frequency tables with number and percentage of observations for each level.

Confidence intervals will be two-sided and constructed at a confidence level of 95%. Statistical tests will be performed at a significance level of 5%, and p-values will be two sided.

Study days will be calculated relative to the date of first dose of study product for subjects randomized to Treatment and relative to the date of randomization for subjects randomized to No Treatment. Day 1 will be the first day of study product administration in the study for the subjects randomized to Treatment and the day of randomization for the subjects randomized to No Treatment. The day prior to Day 1 will be Day -1. There will be no Day 0.

Baseline will be the last assessment prior to the first dose of study product for subjects randomized to Treatment and the last assessment prior to the randomization for subjects randomized to No Treatment. For analysis purpose, the date of randomization will be considered as the date of first dose for subjects who are randomized to No Treatment.

Adverse events and Medical History will be coded using Medical Dictionary for Regulatory Activities (MedDRA), Version 21.0. Concomitant medications will be coded using the World Health Organization (WHO) Drug Dictionary (Mar 2018).

Data for all subjects in the clinical database will be included in the data listings. Calculated (derived) variables will be listed as appropriate. All tables, listings, and figures will be programmed using SAS Version 9.3 or higher. A list of proposed statistical tables, listings, and figures is provided in Section 16.0. Any changes from the SAP will be detailed in the CSR.

Effective date: 2018-09-20 12:05

43USCH1702 Statistical Analysis Plan

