5.1 Intent-to-Treat (ITT) Population

Includes all subjects who were randomized based on the as randomized principle (i.e. according to the treatment they were randomized to).

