5.3 Safety Population

Includes all subjects who were treated with *Restylane® Defyne* or randomized to no treatment control group. Subjects are analyzed based on the as treated principle (i.e. according to the treatment actually received).

The primary and secondary effectiveness analyses will be performed using the ITT analysis set. The primary and the first secondary effectiveness analysis will be repeated using the PP analysis set if there is at least a 10% difference in the number of subjects between the PP and ITT sets. The safety evaluations will be performed based on the safety analysis set.

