13.7 Laboratory Assessments

For all women of childbearing potential, a urine pregnancy test will be performed at screening and all injection visits prior to treatment.

The pregnancy test data will be presented by treatment and subject in data listing.

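### SAP 4.0 ends the baseline window at first injection for Defyne but at randomisation for control, and leaves baseline, Day 1 and Week 12 undefined for a Defyne subject who is never injected

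*SAP*

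**What the plan says.** SAP 4.0 (General Analysis Convention) gives two cut-offs for one quantity. In the Defyne arm, "Baseline will be the last assessment prior to the first dose of study product for subjects randomized to Treatment". In the control arm it is "the last assessment prior to the randomization for subjects randomized to No Treatment". Study days follow the same split: "Study days will be calculated relative to the date of first dose of study product for subjects randomized to Treatment", and from randomisation for controls. A substitute is then supplied for one arm only: "the date of randomization will be considered as the date of first dose for subjects who are randomized to No Treatment".

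SAP 3.1.1 defines the primary response as an improvement of at least 1 point from baseline, scored by the Blinded Evaluator "at 12 weeks after last injection for the treatment group or after baseline if randomized to no treatment".

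SAP 5.1 defines ITT: "Includes all subjects who were randomized based on the as randomized principle". The closing paragraph of SAP 5.3 adds: "The primary and secondary effectiveness analyses will be performed using the ITT analysis set".

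**The concern.** Baseline enters the primary endpoint directly. With a 1-point threshold, a one-grade change in the baseline score can turn a non-responder into a responder, or the reverse. In a randomised comparison the baseline should be fixed before allocation in both arms. There is no sham procedure here, so from randomisation onward the subject and the injector can know the assignment. A rule that accepts a later baseline in the Defyne arm only opens a one-sided route for a score to move after allocation.

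The second problem does not depend on bias. The Defyne rule is tied to an event, the first dose, that may never occur for a subject who nevertheless counts in ITT. The SAP met this problem for controls, who also have no first dose, and solved it with the randomisation date. It gives no equivalent for untreated Defyne subjects. The visible plan therefore does not say how those subjects' baseline and time points are derived, and the gap can arise in one arm only.

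**Working it through.** The documents state no figure that rests on the baseline rule, so there is nothing to reproduce. The check has two parts.

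**1. Applying the SAP 4.0 and 3.1.1 rules as written**

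| Case | Baseline | Day 1 | Week 12 |
|---|---|---|---|
| Defyne, injected, no score between randomisation and injection | Pre-randomisation score | First dose | 12 weeks after last injection |
| Defyne, injected, scored again between randomisation and injection | The later, post-randomisation score | First dose | 12 weeks after last injection |
| Control, scored again after randomisation | Still the pre-randomisation score | Randomisation | 12 weeks after baseline |
| Defyne, never injected | Undefined: no first dose | Undefined | Undefined: no last injection |

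Rows 2 and 3 show the asymmetry and row 4 shows the gap. Row 4 is a case the plan allows for: protocol 5.4 counts a subject as enrolled when randomised and/or treated. The safety population (SAP 5.3) admits Defyne subjects only if treated, so the gap concerns the ITT effectiveness analyses.

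**2. Illustration of size**

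From the documents: about 140 subjects (protocol 4.2) and a two-sided 5% test (SAP 4.0). Everything else is assumed, because allocation ratio, response rates and test are not in the visible text. The assumptions are 1:1, 2:1 or 3:1 allocation (Defyne arm 70, 93 or 105); a true response rate p of 10% to 30% in both arms, so no real effect; a fraction f of Defyne baselines re-scored one grade worse; and a pooled z-test.

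*Shift in response rate.* Rise = f × share of re-scored subjects who would otherwise show exactly zero change.
- f = 5%, share 20%: 0.05 × 0.20 = 1 point.
- f = 5%, share 40%: 0.05 × 0.40 = 2 points.
- f = 5%, share 100%: 5 points, the ceiling.

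*False-positive rate, extreme case.* Suppose every re-scored non-responder becomes a responder, so the Defyne rate is p + f(1 − p). Worked example at 1:1, p = 0.20, f = 0.05:
- Defyne rate = 0.20 + 0.05 × 0.80 = 0.24; pooled rate 0.22.
- Null SE = √(0.22 × 0.78 × 2/70) = 0.0700; critical difference = 1.96 × 0.0700 = 0.137.
- SE under the shift = √((0.20 × 0.80 + 0.24 × 0.76)/70) = 0.0699.
- Rejection probability = Φ((0.04 − 0.137)/0.0699) + Φ((−0.04 − 0.137)/0.0699) = 0.082 + 0.006 = 0.088.

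The same formula over the grid, for p = 10% / 20% / 30%:

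| Allocation | f = 0 | f = 5% | f = 10% |
|---|---|---|---|
| 1:1 | 0.05 | 0.128 / 0.088 / 0.073 | 0.326 / 0.197 / 0.141 |
| 2:1 | 0.05 | 0.102 / 0.078 / 0.068 | 0.260 / 0.167 / 0.125 |
| 3:1 | 0.05 | 0.084 / 0.070 / 0.063 | 0.203 / 0.139 / 0.109 |

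For the milder 1- to 2-point rise, the rate stays at about 0.05 to 0.07.

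*Never-injected subjects.* One is 1/70 = 1.4% of the arm at 1:1 and 1/105 = 1.0% at 3:1; five are 7.1% and 4.8%. If they are counted as non-responders and 70% of treated subjects respond (assumed), one to five of them lower the Defyne rate to between 0.70 × 69/70 = 69.0% and 0.70 × 65/70 = 65.0% at 1:1, or between 69.3% and 66.7% at 3:1. This works against Defyne.

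**The case against.** The strongest reply is that the bias route needs two things the visible text does not show: a gap between randomisation and injection, and a repeat of the primary score within it. The protocol synopsis places the Defyne injection on Day 1, and SAP 4.0 makes the day of randomisation Day 1 for controls, which suggests a single visit. The randomisation and blinding text, the schedule of events and the SAP visit sections are not visible and may fix the order of procedures. The primary variable definition (SAP 9.1) is cut off, so an endpoint-specific baseline cannot be excluded. This stands: bias is possible under the wording but not shown.

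A reader might infer that Defyne baselines are scored by someone who knows the allocation. The documents do not support that. The primary assessor is a Blinded Evaluator, protocol 5.4 keeps identifying source documents from Blinded Evaluators, and the visible text does not say who scores baseline. All that can be said is that the subject and injector can know the assignment at that time.

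A reader might also infer that never-injected Defyne subjects have no baseline data. That goes too far: a pre-randomisation score probably exists, and the gap is in the rule. SAP 11.1 breaks off where the ITT missing-data rule begins, and baseline observation carried forward is among the SAP acronyms, so some handling was probably written. Carrying a baseline forward would still need a defined baseline.

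It is tempting to cite the pregnancy test as a route to non-injection after randomisation. SAP 13.7 says "a urine pregnancy test will be performed at screening and all injection visits prior to treatment", which does not place the test after randomisation, so this point does not rely on it.

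Finally, re-scoring could go the other way and lower Defyne response, and the two problems can act in opposite directions. That also stands. None of this removes the two cut-offs from SAP 4.0, and same-day treatment does not settle the never-injected case.

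**Conclusion.** The definition is asymmetric on its face, and it is incomplete for one group of ITT subjects. Both follow from the wording of SAP 4.0 read with 3.1.1, 5.1 and 5.3.

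The claim stops there. A bias towards Defyne is conditional on post-randomisation, pre-injection scoring, which cannot be confirmed or excluded from the public documents. The effect on treated subjects is zero if scoring comes before same-day randomisation and injection. The size of any bias cannot be derived: the 1 to 2 points (5 at the ceiling) and the false-positive rates above rest on assumed re-scoring, response rates, allocation and test, and the tabulated rates are the extreme case. The never-injected gap is certain as a matter of wording but probably touches few subjects, each about 1.0% to 1.4% of the Defyne arm.

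Severity is low to moderate, with moderate confidence. It is worth correcting because the correction is nearly free.

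**What to change.** In SAP 4.0:

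- Define the effectiveness baseline in both arms as the last assessment before randomisation, made by the Blinded Evaluator for the primary scale.
- For a subject randomised to Defyne and never injected, set Day 1 to the date of randomisation and count Week 12 from that date, as is in effect already done for controls. Cross-refer to this in SAP 3.1.1.
- If a last-before-injection value is wanted for the safety examinations, keep it as a separately named variable.

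With this rule, no post-randomisation score can become a baseline in either arm (f = 0 in the working above), and every randomised subject with a pre-randomisation assessment has a baseline.

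The cost is a few sentences of SAP text and the matching derivation code, with no extra visits or subjects. If the procedures already place Blinded Evaluator scoring before same-day randomisation and injection, no treated subject's result changes.
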